### 9.2.2. Hypothesis

Sarcopenia will influence prognosis, treatment response and adverse events in patients included in the PEACE-6 vulnerable trial.

### 9.2.3. Methods

#### Patients

This ancillary study will be proposed to centres on a voluntary basis. All patients in the centre will be proposed this ancillary study, to avoid recruitment bias. Patients will be prospectively included.

#### Clinical data

A complementary clinical evaluation will be performed by investigators and recorded in the eCRF at each timepoint, from Screening to End of treatment:

- Abdominal circumference, weight and height and body mass index (BMI)
- Maximum handgrip strength using a hand dynamometer, which should be measured sitting down, on a chair with no arm rest. The following instructions should be given to the patient before measurement: "I want to measure your hand grip strength. You can bend your underarm to an angle of 90 degrees. Your arm is not allowed to touch the trunk. Your shoulders should be relaxed. When I say "squeeze", you have to squeeze as hard as you can until I say stop. You might not feel any displacement of the handles, the strength of your grip is displayed on the meter. The measurement will be repeated two times. After each measurement the muscles are allowed to relax for a while. If you experience pain or any discomfort, we will not continue the measurement."

The highest value of the two measurements will be recorded.

### **9.2.4. Statistical analysis**

A descriptive analysis will first be performed to describe proportion of sarcopenic vs non-sarcopenic patients in the population, results of questionnaires, clinical and radiological evaluations.

The prognostic value of sarcopenia in patients will be evaluated by comparing Kaplan–Meier overall survival (OS) curves with the log rank test. Second, a Wilcoxon-Mann-Whitney test will be used to compare the distribution of overall survival between sarcopenic and non-sarcopenic patients.

The predictive value of sarcopenia will be evaluated by comparing rate of response (proportion of complete and partial responses) in sarcopenic and non-sarcopenic patients. A waterfall plot will be generated to compare the two populations. Similarly, to overall survival, Kaplan-Meier progression-free survival curves will be compared with the log rank test, and the distribution using a Wilcoxon-Mann-Whitney test.

Finally, the rate of adverse events (global and severe i.e. grades 3-5) will be compared in sarcopenic vs non-sarcopenic patients.

Sarcopenia evaluated by CT will be correlated to questionnaire and clinical evaluation. Prognostic and predictive values of the questionnaires and clinical tests will be evaluated in the same way as sarcopenia calculated by CT, and compared to CT results.

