### 2.2. Secondary objective(s)

The key secondary objectives of PEACE-6 Vulnerable are:

- To assess the efficacy of ADT + darolutamide vs ADT + placebo in terms of:
  - Castration-resistant prostate cancer-free survival
  - Clinical progression-free survival (cPFS)
  - Overall survival
- To assess the safety profile of the ADT + darolutamide combination.

Other secondary objectives:

- Time to worsening in prostate cancer-related urinary symptoms
- Time to next symptomatic skeletal event
- Prostate specific antigen (PSA) response
- Prostate cancer-specific survival
- To assess the effect of ADT + darolutamide on subsequent lines of therapy
- To evaluate the evolution of quality of life and geriatric status in individuals during the treatment period
- To evaluate the impact of sarcopenia on survival and treatment response.

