### 3.2.2. Secondary endpoint(s)

#### Key secondary endpoints:

- Castration-resistant prostate cancer (CRPC)-free survival, defined as the time from randomisation to onset of CRPC according to PCWG3 criteria, or death, whichever occurs first.
- Clinical progression-free survival, defined as time from randomisation to first occurrence of any one of the following:
  - Cancer pain deterioration (2-point deterioration from baseline according to the Brief Pain Inventory - Short Form [BPI-SF] questionnaire, or initiation of opioid therapy, or a  $\geq 30\%$  increase in opiate use),
  - Any deterioration of physical function measured using the 4-IADL assessment tool,
  - A deterioration in ECOG performance status of at least 2 points from baseline,
  - Death from any cause.
- Overall survival, defined as the time from randomisation to the time of death from any cause. For subjects alive at the time of analysis, data will be censored on the last date the subject was known to be alive or lost to follow-up or withdraw consent.
- Toxicity will be evaluated according to version 5 of the National Cancer Institut - Common Terminology Criteria for Adverse Events (NCI-CTCAE v5.0).

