#### Other secondary endpoints

- Time to worsening in prostate cancer-related urinary symptoms, defined as an increase from baseline of greater or equal to 8 points in the urinary symptom scale/score (PRURI) measured using the prostate cancer module of the European organisation for research and treatment of cancer (EORTC) quality of life questionnaire (QLQ) (EORTC-QLQ-PR25).
- Time to next symptomatic skeletal event, defined as the time from randomisation until first occurrence of one of the following: a symptomatic fracture, radiation or surgery to bone or a spinal cord compression (PCWG3 criteria).

**Note:** *The occurrence of these events will be determined by investigator evaluation. No systematic X-Ray will be performed.*

- Complete PSA response (defined as PSA  $\leq$  0.2 ng/ml) at 6 months.
- Prostate cancer-specific survival, defined as the time from randomisation to the date of death due to prostate cancer (deaths due to other causes will be censored).
- Time to deterioration for EORTC QLQ-PR25 symptom subscales, defined as the first decline in the HRQoL score from baseline equal to or greater than the minimally important difference (MID; a measure of clinical significance) defined as half the standard deviation of the baseline value for each subscale.
- Time to first subsequent systemic anti-cancer therapy (SACT) defined as the time from randomisation to the date of initiation of any SACT for CRPC, following initiation of the study treatment.
- Efficacy of subsequent SACT will be assessed according to rPFS, OS, and PFS after next line of treatment (PFS2); defined as the time from randomisation to second objective disease progression, or death from any cause, whichever first.
- Health related quality of life will be evaluated using the EORTC-QLQ-C30, EORTC-QLQ-PR25 and BPI-SF questionnaires.
- Geriatric status will be evaluated using the Geriatric Core Dataset (G-Code) assessment.
- Impact of sarcopenia on overall survival will be evaluated by comparing the distribution of overall survival between sarcopenic and non-sarcopenic patients.
- Impact of sarcopenia on treatment response will be evaluated by comparing rate of response in sarcopenic and non-sarcopenic patients.

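### Section 9.2.4 adds to valid log-rank tests a Wilcoxon-Mann-Whitney test that ignores censoring in OS and PFS, and calls a comparison that makes no use of treatment arm predictive

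*Protocol*

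**What the plan says.** Protocol section 2.2 lists among the other secondary objectives "To evaluate the impact of sarcopenia on survival and treatment response". Section 3.2.2 turns the survival part into an endpoint, evaluated by "comparing the distribution of overall survival between sarcopenic and non-sarcopenic patients".

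Section 9.2.4 gives the methods:

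- **OS, first test.** "The prognostic value of sarcopenia in patients will be evaluated by comparing Kaplan–Meier overall survival (OS) curves with the log rank test".
- **OS, second test.** "a Wilcoxon-Mann-Whitney test will be used to compare the distribution of overall survival between sarcopenic and non-sarcopenic patients".
- **Response.** "The predictive value of sarcopenia will be evaluated by comparing rate of response (proportion of complete and partial responses) in sarcopenic and non-sarcopenic patients".
- **PFS.** "Kaplan-Meier progression-free survival curves will be compared with the log rank test, and the distribution using a Wilcoxon-Mann-Whitney test".

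Section 3.2.2 defines OS as a censored endpoint: "For subjects alive at the time of analysis, data will be censored on the last date the subject was known to be alive". Table 5 in section 10.3.2 gives the censoring rules for rPFS. Section 9.2.4 does not say how censored times enter the Wilcoxon-Mann-Whitney test, names no censored-data version, and mentions neither treatment arm nor an interaction. The reference list cites the test under its plain name.

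**The concern.** There are two separate problems.

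**Censoring.** An ordinary Wilcoxon-Mann-Whitney test ranks numbers. With censored survival times the analyst must either rank the censored times as if they were deaths or leave living patients out. Take a cut at month 75: a man randomised at month 58 and still alive contributes 75 − 58 = 17 months and is ranked as a worse outcome than a man who died at 30 months. The plan does not say which of its two tests decides, and the endpoint wording in section 3.2.2 echoes the Wilcoxon sentence rather than the log-rank one. If the two disagree, either could be reported.

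**The word predictive.** In a placebo-controlled trial, a predictive marker is one that changes the treatment effect. A comparison of sarcopenic with non-sarcopenic patients that leaves out arm contains no treatment effect to be changed. A published claim that sarcopenia predicts benefit from darolutamide could not rest on it. Section 9.2.4 extends the same approach to the questionnaires and clinical tests, so the label would spread to them.

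**Working it through.** **Inputs from the Protocol.** Section 10.1 gives the accrual (18, 50 and 53 patients in the first three years, then 179 over 24 months), the expected 197 rPFS events at month 75, and a drop-out hazard of 0.014, read here as per month. Section 1.2 gives a median OS of 36.5 months on ADT alone in a cited trial. Section 9.2.4 states no sample size, effect size or power, so it has no figure of its own to reproduce. As a check that the section 10.1 inputs are read correctly, the Schoenfeld formula for HR 0.65, two-sided 0.05 and 85% power gives 194 events and Freedman's gives 200. The Protocol's 197 lies between them.

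**Assumptions.** Half the patients sarcopenic; exponential OS; 150 or 300 sub-study patients (centres join voluntarily, section 9.2.3); OS cut at month 75; hazard ratios, unequal drop-out rates and response rates as stated below. None of these is in the Protocol.

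**Step 1: power.** 150 patients, HR 1.6, median OS 36 months in non-sarcopenic patients, no drop-out, about 42% censored:

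| Test | Power |
|---|---|
| Log-rank | 59% |
| Wilcoxon-Mann-Whitney, all observed times | 44% |
| Wilcoxon-Mann-Whitney, deaths only | 10% |

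At HR 1.5, 300 patients, drop-out 0.014 per month in both groups:

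| Median OS | Log-rank | Wilcoxon, observed times | Wilcoxon, deaths only |
|---|---|---|---|
| 24 months | 75% | 50% | 15% |
| 36.5 months | 64% | 37% | 9% |
| 48 months | 57% | 27% | 7% |

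**Step 2: false positives, no true OS difference.**

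| Censoring pattern | Log-rank | Wilcoxon, observed times |
|---|---|---|
| Equal in both groups | about 5% | about 5% |
| Drop-out 0.007 vs 0.028 per month, 150 patients, median OS 24 / 36.5 / 48 months | about 5% | 59% / 74% / 83% |
| Sarcopenia prevalence rising from 14% to 74% over accrual, 150 patients | 5% | 29% |

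The last two rows are deliberately strong cases. They show the mechanism; they are not an expected error rate.

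**Step 3: the predictive label.** Assume 75 patients per arm-by-sarcopenia cell (150 per sarcopenia group) and use normal approximations.

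*Purely prognostic marker.* Response is 50% on placebo and 60% on darolutamide in non-sarcopenic patients, 30% and 40% in sarcopenic patients. The treatment effect is 10 points in both groups, so the interaction is 0. Ignoring arm, the rates are 55% and 35%.

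- SE = √(0.55×0.45/150 + 0.35×0.65/150) = 0.0563
- z = 0.20/0.0563 = 3.55
- The comparison without arm rejects about 94% of the time; an interaction test rejects 5%.

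*Opposite treatment effects.* Response is 40% and 60% in non-sarcopenic patients, 60% and 40% in sarcopenic patients. Ignoring arm, both rates are 50%, so that comparison rejects 5%.

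- Interaction = −0.20 − 0.20 = −0.40
- SE = √(4×0.24/75) = 0.113
- |z| = 3.54, so the interaction test rejects about 94% of the time.

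The planned comparison is therefore positive when nothing is predictive and silent when the marker is strongly predictive.

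**The case against.** The strongest reply is that section 9.2.4 names the log-rank test first. That test is valid under non-informative censoring, and the prognostic conclusion can rest on it. This stands. A reader might infer that neither the prognostic nor the predictive conclusion could be valid; for prognosis the documents do not support that.

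A reader might also infer that the Wilcoxon-Mann-Whitney test has a generally inflated error rate. It does not: with equal censoring it holds about 5%, and nothing in the Protocol suggests a large drift in prevalence or a fourfold difference in drop-out. What remains in every case examined is lost power.

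The month-75 cut is an assumption. Section 9.2.3 dates only the transfer of CT images, and follow-up runs to 10 years per patient. At about month 180 without drop-out, only about 4–7% of times are censored at HR 1.6, yet power is still roughly 68–70% against 80%. Timing changes the size of the loss, not its direction.

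On the predictive label, the objective speaks of impact on survival and treatment response, and the endpoint compares response rates between the two groups. The comparison answers that endpoint. Neither claims that sarcopenia modifies the darolutamide effect, so the fault lies in the label. That the arms are pooled is inferred from the section's silence on arm. Arm is randomised and sarcopenia is read from baseline CT, so arm is not expected to confound the comparison. Adverse events come in a separate paragraph and are not called predictive.

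Finally, the sub-study is ancillary, and section 10.3.7 treats endpoints outside the key secondary ones as exploratory, without multiplicity adjustment. The second test spends no controlled alpha.

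**Conclusion.** The point holds in a limited form. Section 9.2.4 specifies, twice, a test unsuited to right-censored data alongside one that is suited. The established cost is power: about 44% against 59% in the main scenario, under the assumed HR 1.6, 150 patients, median OS 36 months and month-75 cut. False positives are a conditional risk that depends on censoring or entry time differing by sarcopenia status.

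The response and PFS comparisons, as described, can show prognosis only. The 94% and 5% figures rest on assumed response rates, but the logic behind them does not.

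The consequence is confined to a non-key secondary objective analysed as exploratory. The primary and key secondary analyses are unaffected.

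**What to change.** In section 9.2.4:

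1. Delete the Wilcoxon-Mann-Whitney tests on OS and PFS, or replace them with a censoring-adjusted version (Gehan or Peto) named as such.
2. State that the log-rank test, with a Cox hazard ratio and its confidence interval, carries the prognostic conclusion.
3. Relabel the response and PFS comparisons as prognostic. If a predictive claim is wanted, add a model with arm, sarcopenia and their interaction, report the interaction with its confidence interval, and call it exploratory.
4. Apply the same wording to the questionnaires and clinical tests, which the section says are evaluated in the same way.

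This replaces one short section and needs no new data. The only drawback is that an interaction estimate from a voluntary sub-study of at most 300 patients will be imprecise, and the text should say so. Further stratification by LATITUDE risk and ECOG is optional.

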## 10. DESCRIPTION OF STATISTICAL METHODS

The statistician will produce an initial statistical analysis plan before the inclusion of the first patient (version n°1). This document will be validated by the Steering Committee. The SAP may be revised during the course of the trial in case of substantial modification of the protocol or following recommendations of the Independent Data Monitoring Committee (IDMC). Any revision of the SAP will be validated by the Steering Committee.

### 10.1. Statistical hypothesis and sample size determination

The primary evaluation criterion/endpoint for this study is radiographic progression-free survival (Section 3.2.1).

Assuming a median rPFS of 12 months for the control group, a planned sample size of 300 subjects will be required to provide an 85% power to detect at least a HR of 0.65 (median rPFS 12 months in the standard arm versus 18.5 months in the experimental arm) at a 2-tailed significance level of 0.05 and a drop-out hazard rate in both arms of 0.014 (i.e. a maximum 19.3% drop-out rate at the end of study corresponding to non-evaluable or study withdrawal patients).

The number of **randomised patients will be 300 patients** (150 patients per arm). The dropout rate will be monitored during the study and in case of increased drop-out the sample size may be adjusted accordingly.

Based on the randomization rates observed since the inclusion of the first patient and the projected rates according to the opening of investigator sites (see below), patient inclusion-randomisation is expected to be complete in 60 months.

	Number of randomized patients during the period	Cumulative number (cumulative percentage) of randomized patients at the end of the period
March 2022-Feb 2023	18 pts (1.5 pts/months)	18 (6%)
March 2023-Feb 2024	50 pts (4.167 pts/months)	68 (22.67%)
March 2024-Feb 2025	53 pts (4.4 pts/months)	121 (40.33%)
Mars 2025-Feb 2027*	179 pts (7.5 pts per month)*	300 (100%)*

\*Grounded on projections

An additional 15 months following termination of accrual (i.e. a total of 75 months since the randomization of the first patient) is expected to obtain the required 197 events, assuming that events will follow an exponential distribution with a constant hazard rate.

The final analysis is scheduled 10 years after the last patient inclusion-randomisation.

 Based on data from the control arm of the LATITUDE trial (Fizazi, 2017), and taking into account that (i) patients with oligo-metastatic disease (low risk patients) will not be enrolled, and (ii) some patients are expected to die from other causes before they reach a progression endpoint, making the median rPFS probably shorter than that seen in the LATITUDE trial

## 10.2. Trial populations to be analysed

- Intent-to-treat (ITT) population: all randomised participants
- Safety population: participants who took at least one dose of trial treatment/intervention

For primary and secondary efficacy endpoints, the analysis will be performed on the ITT population, i.e. all randomised patients will be included, whether eligible or not, compliant or not. Patients will be analysed according to their randomisation arm, regardless of the actual treatment received.

Safety analyses will be performed on the safety population. Patients will be analysed according to the treatment received, regardless of the arm to which they were randomised.

## 10.3. Statistical analysis plan

### 10.3.1. *Demographic and other baseline characteristics*

Descriptive statistics will be used to summarize demographics, medical history and baseline characteristics by treatment group. The number of patients in each of the analysed study populations will be described. Unless otherwise specified, all continuous endpoints will be summarized using descriptive statistics, which will include the number of subjects with a valid measurement (n), mean, standard deviation (SD), median, minimum, and maximum. All categorical endpoints will be summarized using frequencies and percentages.

### 10.3.2. *Primary efficacy endpoint analysis*

The primary endpoint is radiographic PFS, defined as the time from randomisation to radiographic progression or death by any cause, whichever occurs first. Radiographic PFS will be right-censored according to the rules shown in Table 5.

**Table 5. Censoring rule for primary analysis of radiographic progression-free survival**

Censoring situation	Date of censoring
No baseline assessment	Date of randomisation
No post-baseline assessment and no death prior to first scheduled assessment	Date of randomisation
No radiographic progression or death on study	Date of last tumour assessment
Withdrawn from the study without documented radiographic progression	Date of last tumour assessment

The primary analysis for the rPFS endpoint will be done considering the first radiographic progression observed under study (even if this first radiographic progression is observed under a subsequent line of therapy). As a sensitivity analysis, in case of initiation of a subsequent line of therapy before observing a radiographic progression, the data will be censored at the time of initiation of the salvage treatment.

The final analysis of the primary endpoint will be event-driven, to be performed when at least 197 patients have experienced radiographic progression or death.

Inference for the primary endpoint will be assessed using a two-sided stratified log-rank statistic as the primary analysis. The analysis on stratification factor at randomisation: LATITUDE risk criteria (high risk versus low risk) and ECOG performance status score (0 or 1 vs 2).

A patient is considered as high risk according to the LATITUDE criteria if he has at least two of the three following high-risk factors associated with poor prognosis: a Gleason score of 8 or more (on a scale of 2 to 10, with higher scores indicating more aggressive disease), at least three bone lesions, and the presence of measurable visceral metastasis. He is otherwise considered as low risk ([Fizazi, 2017](#)).

In case the stratification factor does not have sufficient number of patients (less than 3%) and the inferential analyses would be negatively impacted, the stratification factor will not be included as a stratification factor in this analysis.

The proportional hazard assumption will be assessed graphically by plotting log (-log[estimated survival distribution function]) against log(survival time). The resulting graphs should have approximately parallel lines when the assumption holds. If the proportional hazards assumption is reasonably met, then a stratified Cox proportional hazard model will be used to estimate the treatment effect using Hazards Ratio (HR) and its two-sided 95% confidence interval (95%CI). If the proportional hazards assumption is violated, then the inference remains statistically valid for testing equality in survival distributions. In addition, rPFS will be descriptively summarized using Kaplan-Meier methodology, including medians and two-sided Rothman's 95%CI ([Kaplan, 1958](#); [Rothman, 1978](#)).

Stratification factors will include:

- LATITUDE risk criteria (high risk versus low risk, [Fizazi, 2017](#))
- ECOG performance status score (0 or 1 vs. 2).

If final analysis of the primary endpoint meets the pre-specified hypothesis (see Section 10.1), an additional sensitivity analysis of rPFS will be performed using the results of a centralised disease evaluation by an independent review committee (IRC).

All the other secondary time to event endpoints (namely, CRPC-free survival, clinical progression-free survival, time to worsening in prostate cancer-related urinary symptoms, time to next symptomatic skeletal event, prostate cancer specific survival and overall survival, time to first subsequent SACT and time to second subsequent SACT) will be analysed using the same methods as the primary endpoint (stratified two-sided log-rank test, stratified Cox proportional hazards models). Secondary endpoints will be analysed according to the investigators' assessment of response. Censoring rules for these endpoints will be detailed in the SAP.

The median follow-up will be estimated using the inverse Kaplan-Meier method ([Schemper, 1996](#)).

